## When to use ActiGraph

The ActiGraph activity tracker will only be used in the main part of the trial.

### Phase 2 patients

Patients already enrolled in arm 3 from phase 2, NN7415-4310 (explorer 4), before the treatment pause, should not wear the physical activity tracker.

### Remaining patients

The instruction below includes new patients, patients currently in the trial and patients enrolled from NN7415-4322 (explorer 6).

#### Baseline measurement:

- Patients who already have a baseline measurement either from NN7415-4322 (explorer 6) or this trial (patients who started treatment before the treatment pause) will not have a new baseline measurement taken. Patients who were in screening at the time of the treatment pause and who are re-starting the trial will have a new baseline measurement taken.
- For new patients or patients who do not have a sufficient baseline measurement from NN7415-4322 (explorer 6), the physical activity tracker will be handed out to the patient at screening (visit 1a). The patients will be instructed to wear the tracker for approximately two consecutive weeks or as much as possible to establish a baseline value. The patient will be instructed to return the activity tracker at visit 2a.

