### 4.3.3 Exploratory endpoints

| Endpoint title                                                      | Time frame                                         | Unit  |
|---------------------------------------------------------------------|----------------------------------------------------|-------|
| Patient reported outcomes                                    |                                                    |       |
| Patient preference assessed by questionnaire                        | Week 24                                            | %     |
| Change in patient's treatment burden using the Hemo-TEM total score | From baseline (week 0 a ) until week 24 | Score |

| Endpoint title                                                         | Time frame                                                                                         | Unit     |
|-------------------------------------------------------------------------------|-----------------------------------------------------------------------------------------------------------|-----------------|
| Change in PROMIS Short Form v2.0 -Upper Extremity 7a                          | From baseline (week 0 a ) until week 24                                                        | Score           |
| Change in PROMIS Numeric Rating Scale v.1.0 – Pain Intensity 1a               | From baseline (week 0 a ) until week 24                                                        | Score           |
| Change in Haem-A-QoL total score                                              | From baseline (week 0 a ) until week 24                                                        | Score           |
| Change in Haem-A-QoL physical health domain score                             | From baseline (week 0 a ) until week 24                                                        | Score           |
| Physical activity measured by accelerometer                            |                                                                                                           |                 |
| Change in time spend in moderate to vigorous physical activity (MVPA) per day | From baseline to end of the main part (week 24 for the on-demand arm and week 32 for the concizumab arms) | Minutes per day |

aDefined as time of randomisation to on-demand administration or time of start of the new concizumab dosing regimen.

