#### Efficacy Measurement:

- To investigate the effect of concizumab daily PPX on patients physical activity, the patients will be instructed to wear the physical activity tracker for eight consecutive weeks or as much as possible at the end of the patient's main part of the trial (weeks 16–24 for arm 1 and weeks 24–32 for arm 2 and 4 patients).
- Patients who are restarting the trial at visit 2a and already have an ActiGraph measurement (from before the treatment pause) will be asked to repeat the ActiGraph activity measurement at visit 9a.
- Arm 1 patients who have already completed the main part of the trial and is re-starting the trial at visit 9a will not be asked to repeat any measurements.

[Table 11](#) shows an overview of when to use the ActiGraph physical activity tracker in this trial.

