**Table 11 Physical Activity Tracker handout overview**

| Treatment arm | Patients trial history                                                                     | Baseline Measurement | Wear-period in trial |
|---------------|--------------------------------------------------------------------------------------------|----------------------|----------------------|
| Arm 1         | Patients with no or insufficient baseline measurement who will start the trial at visit 1a | Visits 1a – 2a       | Visits 7a – 9a       |
|               | Patients with baseline measurement who will start the trial at visit 1a                    | N/A                  | Visits 7a – 9a       |
|               | Patients who will re-start trial at visit 9a                                               | N/A                  | N/A                  |
| Arms 2 and 4  | Patients with no or insufficient baseline measurement who will start the trial at visit 1a | Visits 1a – 2a       | Visits 9a – 10a      |
|               | Patients with baseline measurement who will start trial at visit 1a                        | N/A                  | Visits 9a – 10a      |
|               | Patients who will re-start trial at visit 2a                                               | N/A                  | Visits 9a – 10a      |
| Arm 3         | Patients who re-start the trial in arm 3                                                   | N/A                  | N/A                  |

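### In patients randomised before the pause, MVPA change is measured over a much longer and later period in arm 2 than in arm 1, so part of a shared activity change can be attributed to concizumab

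*Protocol*

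**What the plan says.** Protocol section 4.3.3 lists change in daily MVPA time as an exploratory endpoint, with the time frame "From baseline to end of the main part (week 24 for the on-demand arm and week 32 for the concizumab arms"). The other change endpoints in that section run from week 0, which footnote a ties to randomisation to on-demand or to the start of the new regimen. The MVPA row carries no such footnote.

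Section 9.2.5 gives the purpose of the outcome wear period: "To investigate the effect of concizumab daily PPX on patients physical activity". The planned windows are "weeks 16–24 for arm 1 and weeks 24–32 for arm 2 and 4 patients". Three rules decide what patients enrolled before the pause contribute:

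- **Baseline:** "patients who started treatment before the treatment pause) will not have a new baseline measurement taken".
- **Outcome, patients restarting at visit 2a who already have a tracker measurement:** they "will be asked to repeat the ActiGraph activity measurement at visit 9a". Table 11, in the arms 2 and 4 row "Patients who will re-start trial at visit 2a", gives no new baseline and a wear period from visit 9a to 10a.
- **Outcome, arm 1 patients who had completed the main part:** those "re-starting the trial at visit 9a will not be asked to repeat any measurements". Table 11 shows no baseline and no wear period for them after restart.

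Patients who were only in screening at the pause do get a new baseline, and so do new patients without a sufficient explorer 6 measurement.

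**The concern.** Among patients randomised before the pause, the arm determines the measurement period. The arm 2 change spans the initial regimen, the pause and at least 24 weeks of the new regimen. The arm 1 change ends at week 24 of on-demand treatment. Season, pandemic restrictions, ageing and joint progression can move activity in both arms over that time, and earlier concizumab exposure can move it in arm 2. Because arm and period coincide in these patients, adding a pre-/post-pause main effect to a model would not separate them.

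The endpoint is meant to show an effect of concizumab. A reader of the arm comparison would take the difference as that effect, although part of it could be calendar time. The error can go in either direction.

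**Working it through.** The documents give no SD, effect size or sample size for MVPA, so there is no planned figure to reproduce. The check has three steps.

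**1. Intervals.** Inputs from the Protocol: phase 3 began in October 2019 (section 3.2); the pause ran from March to August 2020 (section 4.3.2.2, footnote c); the wear windows are those in section 9.2.5. Assumptions: pre-pause randomisation between 22 October 2019 and 1 March 2020; baseline wear centred 10 days before randomisation; pause of 1 March–31 August or 16 March–15 August 2020; restart the day after the pause ends.

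- Arm 1: mid-window is randomisation + 20 weeks, so the interval is 20 weeks + 10 days ≈ 21 weeks.
- Arm 2 restarter: mid-window is restart + 28 weeks. Longest case: 12 October 2019 to 16 March 2021 ≈ 74 weeks. Shortest case: 20 February 2020 to 28 February 2021 ≈ 53 weeks.
- The two outcomes lie 32–53 weeks apart in calendar time.

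A baseline taken from explorer 6 would be older and would lengthen the interval in either arm. A restart later than the first possible day would lengthen it in arm 2.

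**2. How much of a shared change reaches the contrast.** Section 5.1 says that arm 1 patients continued on-demand treatment and reporting until restart. Under the same dates, their week 16–24 window runs from 11 February–7 April 2020 at the earliest to 21 June–16 August 2020 at the latest, so 39–100% of it lies inside the pause. Arm 1 can therefore capture some of the change.

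Let D be the shared change present when restarters are measured, c the fraction of D already present in arm 1's window, and p2 and p1 the pre-pause shares of arms 2 and 1. Taking changes shared by patients randomised after the pause to cancel:

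bias in (arm 2 − arm 1) = (p2 − p1·c)·D

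With p1 = p2:

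- p = 1, c = 0: 1.00·D
- p = 0.5, c = 0: 0.50·D
- p = 0.5, c = 0.5: 0.25·D
- p = 0.25, c = 0.5: 0.125·D
- c = 1: 0

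A temporary dip, present in arm 1's window but over before restarters are measured, would bias the contrast the other way, in favour of concizumab.

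**3. Illustrative size.** Table 2 gives 17 patients in arm 1 (9 + 8) and 34 in arm 2 (18 + 16). Change scores are simulated as N(0,1) with no treatment effect and compared by a two-sample t-test at two-sided 5%. Pre-pause arm 2 patients are shifted by d SD and pre-pause arm 1 patients by c·d. With half of each arm pre-pause, d = 0.5 gives a bias of 0.5 × 0.5 = 0.25 SD at c = 0 and 0.125 SD at c = 0.5. Rejection rates:

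| Captured by arm 1 (c) | d = 0.25 | d = 0.5 | d = 0.75 | d = 1.0 |
|---|---|---|---|---|
| 0 | 6.9% | 12.2% | 20.7% | 31.6% |
| 0.25 | 5.9% | 8.9% | 13.7% | 19.5% |
| 0.5 | 5.3% | 6.5% | 8.4% | 10.6% |

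At c = 0.5 the same four shifts give 6.0%, 8.3%, 12.4% and 16.9% if 70% are pre-pause, and stay below 6% if 30% are. With no shift the rate is 5%. Restricting the contrast to patients randomised after the pause returns it to about 5%.

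**The case against.** The strongest points on the other side are these.

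- **Arm 1 is not blind to the pause.** A reader might infer that every activity change shared by the arms over the pause is counted as a concizumab effect. The documents do not support that: pre-pause arm 1 patients were observed into the pause, and patients randomised after it follow the same baseline rules in both arms. This stands, and it is why the bias is only a fraction of D.
- **No MVPA test is planned in these documents.** Section 10.3 confines hierarchical testing to bleeds and two SF-36v2 scores. The rejection rates above are therefore a yardstick, not the trial's error rate. The largest rates also need no capture by arm 1, which fits poorly with section 5.1. This stands.
- **The governing SAP is not available.** Section 10.3.3 defers exploratory analyses to the SAP. The SAP supplied covers the 56-week cut-off only, does not list MVPA in its Appendix 2, and sends main-part analyses to the primary cut-off SAP. A reader might infer that the sponsor has no safeguard; all that can be said is that none appears here. The pre-/post-pause sensitivity analyses in section 10.3.1 concern treated bleeds.
- **Keeping the old baseline is defensible.** It precedes randomisation and treatment in both arms. A new one at restart would follow the initial regimen, standard of care and the pandemic in arm 2 alone. This stands as a reason not to insist on re-baselining. It does not make the two intervals comparable.
- **The endpoint is exploratory.** This limits the consequence, and the cost of the remedy is correspondingly small.

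**Conclusion.** The concern holds in a limited form. Followed as written, section 9.2.5 and Table 11 give pre-pause patients a baseline-to-outcome interval of roughly 53–74 weeks in arm 2 against about 21 weeks in arm 1, under the assumed dates. Part of a shared activity change can then be attributed to concizumab, in proportion to the restarter share of arm 2 and to what arm 1's window had not captured. Changes after the pause, and effects of earlier concizumab exposure, lie outside what pre-pause arm 1 could capture.

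The size is not derivable from the documents: the pre-pause shares, the shift and the captured fraction are all assumptions. About 12% (no capture) and 6.5% (half captured) against a nominal 5% are illustrations for half the patients pre-pause and a 0.5 SD shift. The point affects one exploratory endpoint and leaves the confirmatory analyses untouched. It is worth correcting because the correction is cheap.

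**What to change.** 1. In section 4.3.3 and in the analysis of this endpoint, state which baseline is used for patients who restart.
2. Present MVPA change separately for patients randomised before and after the pause, and show the baseline-to-outcome interval by arm.
3. Add the arm 1 versus arm 2 contrast in patients randomised after the pause. Make it the contrast to rely on for a treatment effect or, at minimum, a prespecified sensitivity analysis. Note beside it that the wear windows still differ (weeks 16–24 against 24–32) and that explorer 6 baselines may be older.

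If the primary cut-off SAP already does this, a cross-reference is enough. The change uses data already collected and needs no extra visits or devices. The downside is fewer patients and lower precision in one exploratory contrast; the number lost is unknown because the documents do not give the split of patients before and after the pause.

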#### Efficacy Measurement:

- To investigate the effect of concizumab daily PPX on patients physical activity, the patients will be instructed to wear the physical activity tracker for eight consecutive weeks or as much as possible at the end of the patient's main part of the trial (weeks 16–24 for arm 1 and weeks 24–32 for arm 2 and 4 patients).
- Patients who are restarting the trial at visit 2a and already have an ActiGraph measurement (from before the treatment pause) will be asked to repeat the ActiGraph activity measurement at visit 9a.
- Arm 1 patients who have already completed the main part of the trial and is re-starting the trial at visit 9a will not be asked to repeat any measurements.

[Table 11](#) shows an overview of when to use the ActiGraph physical activity tracker in this trial.

**Table 11 Physical Activity Tracker handout overview**

| Treatment arm | Patients trial history                                                                     | Baseline Measurement | Wear-period in trial |
|---------------|--------------------------------------------------------------------------------------------|----------------------|----------------------|
| Arm 1         | Patients with no or insufficient baseline measurement who will start the trial at visit 1a | Visits 1a – 2a       | Visits 7a – 9a       |
|               | Patients with baseline measurement who will start the trial at visit 1a                    | N/A                  | Visits 7a – 9a       |
|               | Patients who will re-start trial at visit 9a                                               | N/A                  | N/A                  |
| Arms 2 and 4  | Patients with no or insufficient baseline measurement who will start the trial at visit 1a | Visits 1a – 2a       | Visits 9a – 10a      |
|               | Patients with baseline measurement who will start trial at visit 1a                        | N/A                  | Visits 9a – 10a      |
|               | Patients who will re-start trial at visit 2a                                               | N/A                  | Visits 9a – 10a      |
| Arm 3         | Patients who re-start the trial in arm 3                                                   | N/A                  | N/A                  |

### Instructions to patients

The site staff should instruct the patient according to the following recommendations:

- The physical activity tracker should be worn on the non-dominant arm
- The physical activity tracker should be firmly attached to the wrist and the tracker should not be able to slide up and down when the arm moves
- The patient should wear the physical activity tracker as much as possible, preferably 24 hours per day
- The patient should wear the physical activity tracker as much as possible for approximately eight consecutive weeks between relevant visits
- The physical activity tracker should be returned to the site according to the flowchart in Section 2

The measurements from the physical activity tracker are summarised into daily measures representing different aspects of physical activity.

All safety information and/or other issues judged by the investigator to be related to wearing the activity monitor should be reported by the site directly to the manufacturer ([contact]).

### 9.2.6 Patient-reported outcome questionnaires

This trial includes eight Patient-Reported Outcome (PRO) questionnaires, see [Table 12](#).

PRO questionnaires will be completed, if available in local language, by the patient (not the caregiver) in accordance the trial flow chart in Section 2. PRO-questionnaires will be completed as ePROs by the patient using the same eDiary except for Haem-A-QoL (all countries) and PROMIS (some countries) which will be completed on paper.

At visit 2a and visit 9a, patients must complete the PRO questionnaires on the day of the site visit, preferably before any other assessments. For the remaining visits, patients should preferably complete the PRO questionnaires on the day of the visit before any other assessments.

Patients re-entering the trial after the treatment pause should fill out all forms according to the flowchart in Section 2. For these patients, previous treatment will be defined as the treatment they received during the concizumab treatment pause. The site staff must inform the patients about this 'previous treatment' definition prior to completing the questionnaires.

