| c) Visit will take place after the concizumab exposure levels are available according to in Section 9.2.2                                                                                                                             |
| d) Only patients enrolled after the treatment pause will sign the Informed Consent at visit 1a                                                                                                                                                        |
| e) Only patients enrolled in the trial before the treatment pause and allocated to arm 2, 3 and 4, will re-consent at Visit 2a                                                                                                                        |
| f) Only patients enrolled in the trial before the treatment pause and randomised to arm 1, will re-consent at visit 9a                                                                                                                                |
| g) Only applicable for arm 1 patients, who are receiving concizumab at Visit 9a                                                                                                                                                                       |
| h) Only applicable for patients in arm 2, 3 and 4, who are receiving concizumab at visit 2a                                                                                                                                                           |
| i) Only applicable for patients enrolled in the trial before treatment pause. Site must ensure patients do not violate discontinuation criteria according to Section 8.1 before reinitiating dosing with concizumab                   |
| j) Patients randomised to arm 2 before the treatment pause will not be re-randomised at visit 2a                                                                                                                                                      |
| k) Weight only, except at visit 1 where height is measured                                                                                                                                                                                            |
| l) For patients having concizumab dosing at visit 2a there will be a 24-hour PK session at visit 2a and 9a. Please see details for PK sampling in Section 2.1 . For on-demand patients (arm 1) only the pre-dose sample will be taken |

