### 4.3.2 Secondary endpoints

#### 4.3.2.1 Key secondary endpoints

| Endpoint title                        | Time frame                                                   | Unit  |
|---------------------------------------|--------------------------------------------------------------|-------|
| Health economics               |                                                              |       |
| Change in SF36v2 bodily pain          | From start of treatment (week 0 a ) until week 24 | Score |
| Change in SF36v2 physical functioning | From start of treatment (week 0 a ) until week 24 | Score |

aDefined as time of randomisation to on-demand administration or time of start of the new concizumab dosing regimen

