## Figure 2 Concizumab dosing regimen upon re-initiation of trial

Doses, including the loading dose, given at PK/PD visits (i.e. visit 2a and 9a) will be administered at the site; all other injections may be administered at home by the patient or caregiver.

Prior to visit 2a, patients must be in a non-bleeding state 48 hour prior to the visit however patients are allowed to have treatment for up to 24 hours prior to visit 2a, except for treatment with aPCC and ByClot® where the wash-out is 48 hours prior to visit 2a.

For patients coming from a PPX treatment regimen, a wash-out of aPCC and ByClot® for 48 hours is required. For other factor-containing products, a wash-out of 2 half-lives of the given product is required.

A pre-filled, multi-dose pen-injector for the drug administration will be provided by Novo Nordisk, details can be found in Section [7.1.1](#).

Use of factor-containing products not associated to a bleed is not allowed, except for diagnostic procedures, intramuscular injections (e.g. vaccinations) and minor surgery, e.g. dental treatment, endoscopies etc.

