#### 8.1.1 Temporary discontinuation of concizumab in relation to COVID-19

Regular testing for COVID-19 will not be part of the protocol, but will be done at the investigator's discretion only. Testing should be performed according to the locally recommended testing methodology.

In case a patient is tested positive for ongoing COVID-19 infection prior to the first concizumab dose, then visit 2a/9a (allocation/randomisation visit) should be postponed until a negative COVID-19 result exists or the patient has fully recovered from the COVID-19 infection as judged by the investigator. During the trial, in the case a patient is tested positive for ongoing COVID-19, concizumab should be paused immediately and not restarted until the patient tests negative again or has fully recovered from COVID-19 as judged by the investigator. In the interim period, patients should be treated as per judgement of the investigator.

If access to COVID-19 testing is limited, then the pause and postponement should be based on a strong suspicion, as judged by the investigator.

A positive COVID-19 test, or suspicion of COVID-19, is considered an AE and should be reported as such following the procedures in Section [9.3](#) and [Appendix 5](#).

In case of a suspected thromboembolic event, it is encouraged to perform a COVID-19 test. If a thromboembolic event is diagnosed, COVID-19 testing must be performed. Additionally, analysis for COVID-19 antibodies may be performed; see Section [9.4.6](#).

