### **9.2.1 eDiary**

Novo Nordisk will provide the patient with an eDiary for electronic recording of following assessments:

- Treatment with concizumab, see Section [9.2.2](#)
- Bleeding episodes including treatment of bleeds, see Section [9.2.3](#)

- PRO questionnaires see Section [9.2.6](#)
- Health economic questions see Section [9.8](#)

The eDiary and related support services will be supplied by a vendor working under the direction and supervision of Novo Nordisk.

Patients or patient's caregiver will be trained in the use of the eDiary by the investigator or delegated personnel before entering of any data. The eDiary will be dispensed to the patient at visit 2a (unless an eDiary has already been dispensed). After visit 2a and onwards, data will be entered by the patient or patient's caregiver in the eDiary at home. The patient should bring his eDiary at all visits to ensure the eDiary is working properly. The eDiary will be returned by the patient at the end of trial visit (visit 27a).

For data collected in the eDiary, the investigator must review treatment data, bleeding episodes and specific PRO's, as specified in Section [9.2.6](#). The review should be documented accordingly. It is the responsibility of the investigator to instruct the patient about the timelines for timely completion of the eDiary.

If the investigator finds it necessary to amend or correct eDiary data, the patient must be consulted, and outcome documented prior to requesting the actual data change. A Data Correction Request must be submitted to the eDiary vendor. An audit trail will be maintained.

All data entered will be transferred from the eDiary to an electronic database, where it is kept as a certified copy of the source data by the eDiary vendor. Data entered in the eDiary will upon confirmation of a successful back-up be deleted from the eDiary.

The eDiary will have built in edit checks and reminders, to ensure that all relevant questions are answered. eDiary data transferred to the electronic database will be viewable to relevant trial site staff and Novo Nordisk personnel on a secure, password protected web portal.

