### 10.3.2 Secondary endpoints

#### 10.3.2.1 Key secondary endpoints

The key secondary endpoints are defined in Section [4.3.2.1](#).

The two key secondary endpoints based on SF-36v2 will be analysed including all patients in the FAS where patients contribute with observation time as described under Section [10.3.1](#). In order to incorporate the patients from the original randomisation that have not restarted, statistical analysis will be implemented as a statistical model using multiple imputations where the subjects without any available SF-36v2 measurements at scheduled visits will have their SF-36v2 value imputed from the available information from the treatment group the subject has been randomised to. For

subjects that have no observations on the new dosing regimen, the baseline value before the initial randomisation will be used. Subjects without any post-randomisation measurements contribute to the analysis, as the missing values will be imputed. The analysis will be implemented as follows.

- For all patients the baseline value will be set to either the value obtained just prior to the re-start and if that is missing, the value prior to the initial randomisation.
- In the first step, intermittent missing values are imputed using a Markov Chain Monte Carlo method, in order to obtain a monotone missing data pattern. This imputation is done for each treatment group separately and 1000 copies of the dataset will be generated.
- In the second step, for each of the 1000 copies of the dataset, an analysis of variance model with stratification factors as factors and baseline SF-36v2 value as covariate is fitted to the change in SF-36v2 from baseline to week 4 for each treatment group separately. The estimated parameters, and their variances, from these models are used to impute values at week 4 for subjects in each treatment group, based on stratification factors and baseline SF-36v2.
- In the third step, for each of the 1000 copies of the dataset, missing values at week 8 are imputed in the same way as for week 4 but now also including the SF-36v2 values at week 4 in the model. This stepwise procedure is then repeated sequentially for week 16 and 24 and in each step the SF-36v2 values in previous weeks are also included in the model.
- For each of the complete data sets, the change from baseline to week 24 is analysed using an analysis of variance model with treatment and stratification factors as factors, and baseline SF-36v2 as a covariate.

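### Section 9.2.6 prefers but does not require that the SF-36v2 comes first at visits 2a and 9a, so a compliant score can follow open-label allocation or, in arm 1, the first concizumab dose

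*Protocol*

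**What the plan says.** Protocol Section 4.3.2.1 names two key secondary endpoints, the change in SF-36v2 bodily pain and in physical functioning from week 0 to week 24. Section 10.3 tests both for superiority at 5%, in a hierarchy after the primary endpoint.

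On timing, Section 9.2.6 states that at visits 2a and 9a "patients must complete the PRO questionnaires on the day of the site visit, preferably before any other assessments". The same section has the SF-36v2 completed electronically on the eDiary. Section 9.2.1 hands out the eDiary at visit 2a unless the patient already has one.

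Other events fall on the same visits:

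- **Visit 2a.** The Section 2 flowchart places randomisation here, and Section 8.1.1 labels these visits accordingly ("visit 2a/9a (allocation/randomisation visit) should be postponed"). Section 7.3 makes the trial open label. Patients already in arm 2 are an exception: "Patients randomised to arm 2 before the treatment pause will not be re-randomised at visit 2a" (flowchart footnote j).
- **Visits 2a and 9a.** Under Section 5.2.1, "Doses, including the loading dose, given at PK/PD visits (i.e. visit 2a and 9a) will be administered at the site". For arms 2 to 4 the loading dose falls at visit 2a. For arm 1 it falls at visit 9a (Table 1 and Section 5.2.1), which is also arm 1's week 24.

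Section 10.3.2.1 sets the SF-36v2 baseline to "the value obtained just prior to the re-start and if that is missing, the value prior to the initial randomisation". It applies the observation periods of Section 10.3.1, which end for arm 1 when the new concizumab regimen starts.

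**The concern.** The collection rule is looser than the analysis rule. The analysis presumes a baseline given before re-start or randomisation and an arm 1 week-24 score given before concizumab. The collection rule guarantees only that each score comes from the right day.

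This matters because the outcomes are self-reported, the patient knows his arm, and both endpoints carry confirmatory tests. A baseline given after the patient learns whether he received prophylaxis may differ between arms because of that knowledge, and the baseline adjustment would pass the difference on to the treatment effect. An arm 1 score given after the loading dose lies outside the on-demand period that it is meant to describe.

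**Working it through.** The plan gives no SF-36v2 standard deviation, expected effect or power, so there is no stated figure to reproduce. The first three steps compare texts. The last two only illustrate direction and scale.

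**1. Is the order fixed anywhere?** Section 9.2.6 makes the day mandatory and the order a preference. Randomisation and dosing are not named. The questionnaire rows of the Section 2 flowchart are missing from the text supplied, but its footnotes are present and none places a questionnaire before randomisation or dosing. By contrast, footnote m forbids injecting on the visit day before the concizumab sample is drawn, and Appendix 2 says that laboratory samples should be taken before dosing. The questionnaires have no such rule.

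**2. Is there another baseline to fall back on?** Not for a new patient, as far as the supplied text shows. He receives the eDiary at visit 2a, and the data transferred from the non-interventional study (Section 9, shared assessments) include no questionnaires. Section 10.3.2.1 states no imputation step for a missing baseline.

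**3. Who is exposed?**

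| Group | Baseline at visit 2a | Week-24 score |
|---|---|---|
| Newly randomised, arm 1 | may follow allocation | visit 9a, may follow first dose |
| Newly randomised, arm 2 | may follow allocation or loading dose | on concizumab by design |
| Arm 2, randomised before the pause | follows allocation by design; may follow loading dose | on concizumab by design |
| Arm 1, randomised before the pause | not applicable (re-enters at visit 9a) | at risk only if taken at visit 9a |

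The documents do not say how many patients are in each row.

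**4. Direction.** Let ΔY0 and ΔY24 be the arm 2 minus arm 1 differences in mean baseline and week-24 score, and b the slope of the week-24 score on baseline. The final model is fitted to the change with baseline as covariate, so its baseline coefficient is b − 1. With balanced strata:

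adjusted difference = (ΔY24 − ΔY0) − (b − 1)ΔY0 = ΔY24 − bΔY0.

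- A spurious baseline difference d adds −b × d. With assumed b of 0.5 to 0.7 and d of 1 to 3 points, this runs from −0.5 × 1 = −0.5 to −0.7 × 3 = −2.1 points.
- A dose-related shift e in arm 1's mean week-24 score adds −e.
- Both d and e are arm-level averages, so they shrink in proportion if only some patients complete out of order.

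Assuming that higher scores mean better health, a patient pleased to get prophylaxis or disappointed not to get it makes d positive, and an arm 1 patient who feels better for having been dosed makes e positive. Both reduce the apparent benefit of concizumab. If d or e is negative, the sign reverses.

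**5. Scale relative to trial size.** Table 2 gives 9 + 8 = 17 patients in arm 1 and 18 + 16 = 34 in arm 2. In residual SD units, SE = √(1/17 + 1/34) = 0.297. With no true effect, an assumed shift s in the contrast gives a two-sided rejection probability of Φ(s/SE − 1.96) + Φ(−s/SE − 1.96):

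| s (SD) | 0 | 0.1 | 0.2 | 0.3 |
|---|---|---|---|---|
| Rejection | 5.0% | 6.3% | 10.3% | 17.3% |

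These rejections favour concizumab only if s does. If s runs against it, the cost is power. The difference detectable with 80% power is (1.96 + 0.84) × 0.297 = 0.83 SD, and an adverse shift of 0.2 SD lowers that power to Φ((0.832 − 0.2)/0.297 − 1.96) = Φ(0.17), about 57%.

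**The case against.** The strongest reply is that the preferred order, if followed, already does the job. Completing the questionnaire before every other assessment puts it ahead of the eligibility check at visit 2a and ahead of the pre-dose samples at both visits. On that view the fault is one soft adverb. This is fair as a description, and many sites may well work in that order. But a preference cannot be enforced, and departing from it is not a deviation that anyone would record.

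Second, Sections 10.3.1 and 10.3.2.1 read together arguably exclude an arm 1 score given after the first dose. That stands in principle. In practice it takes a comparison of completion and dose times, which no passage calls for.

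Third, an arm 1 patient at visit 9a already knows that concizumab is about to start, so completing the form before dosing does not remove expectation. This also stands. The rule would remove an effect of the dose and nothing more. Nothing supplied shows that a dose changes pain or functioning on the same day.

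Fourth, the SAP supplied covers only the 56-week evaluation and refers the secondary endpoints to the SAP for the primary analysis cut-off, which was not supplied. That document may contain a derivation rule.

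A reader might also infer that baselines were in fact contaminated, that the SF-36v2 benefit is inflated, or that the data cannot be repaired. The documents support none of these. They show what is permitted and not what sites did, the natural direction reduces the benefit, and scores out of order can be identified wherever times were recorded.

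**Conclusion.** The point holds as a mismatch between collection and analysis. Section 9.2.6 lets a site comply while a newly randomised patient's baseline follows disclosure of his arm, or an arm 1 patient's week-24 score follows his first dose. The SF-36v2 analysis assumes neither occurs.

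No size can be derived from the documents. The range of −0.5 to −2.1 points rests entirely on assumed values of slope and shift, and on every relevant patient being affected. It would be wrong to report it as an estimate of bias in this trial. The sign may well be conservative for the superiority claim, but it is not guaranteed.

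The primary bleeding endpoint is not affected. For arm 2 patients randomised before the pause, only the pre-dose part of a stricter rule could help, because their visit 2a baseline follows allocation whatever the wording. This is a cheap improvement to two confirmatory endpoints and does not undermine the design.

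**What to change.** In Section 9.2.6, replace the preference at visits 2a and 9a with a requirement such as: *The PRO questionnaires must be completed before the IWRS randomisation call at visit 2a (newly randomised patients) and before any administration of concizumab at visits 2a and 9a.*

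Then add to the analysis plan for the primary analysis cut-off:

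- Compare eDiary completion times with the IWRS randomisation time and the first-dose time. Section 7.5 already requires the time of each on-site dose in the medical record.
- Treat an arm 1 week-24 score completed after the first dose as missing in the multiple imputation of Section 10.3.2.1.
- Flag a baseline completed after randomisation and handle it by a prespecified rule, for example a sensitivity analysis without those values. Simply setting it to missing is not enough, because Section 10.3.2.1 gives a new patient no fallback value and no imputation step for baseline.

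The cost is one sentence in the protocol and site instructions, one comparison of times, a slightly longer start to two visits, and perhaps a few flagged or missing values. If the visits have already taken place, the new wording comes too late, but the time check and sensitivity analysis remain possible where times were recorded. They should be labelled post hoc if specified after the results are known.
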